6.4 Privacy, Confidentiality and Data Security

All data will be stored and transferred using a secure server with de-identified information.

We will take steps to keep the participant's personal information confidential. Health information will be kept secure and separate from information which identifies participants. Upon enrollment, participants will be assigned a code that will be used instead of their name, medical record number or other personally identifying information. Electronic files for data analysis will contain only the participant code. The code will be stored at Aravind on a secure server and will only be accessed by study personnel – the PI, study coordinator, or other member of the study team. Access to study-related patient information will be limited only to members of the study team.

Only a small number of researchers related to this study will have direct access to the participant's medical information. Paper files will be stored in locked filing cabinets in restricted access offices at Aravind. Access to data/specimens is restricted to study personnel.

Information may be released to others outside of Aravind who are involved in coordinating or overseeing research, but information which identifies the participant will be kept secure. To ensure the success of this study, Aravind has partnered with University of California, San Francisco (UCSF)'s F.I. Proctor Foundation, which is a center that specializes in ophthalmology research. The coordinating center at UCSF will have access to de-identified information using a code number. UCSF's role is to support Aravind on the data analysis

portion of this study and assisting with the development of consent and study-related materials. UCSF will obtain IRB approval to take part in this study (IRB number: 15-17347).

6.5 Exclusion of Vulnerable Populations

The following populations will not be enrolled in this study: children (18 years and under), pregnant women, decisionally impaired adults, and prisoners.

6.6 Compensation to Participants

There is no additional cost or compensation for the study participant. There will be no compensation for research-related injury.

7. DATA COLLECTION AND MANAGEMENT

7.1 Data Collection and Entry

All data will be collected using hardcopy patient forms at Aravind during baseline and follow-up visits. De-identified data will be uploaded to a Dropbox account in order to share the data with the UCSF study coordinator. De-identified data will be input into a database using double data entry at UCSF.

7.2 Data Consistency, Validity, and Monitoring

Data monitoring reports will be prepared using STATA and Excel. If the forms are not filled out completely, the UCSF study coordinator will contact the person responsible for completing the form to provide the missing data, or clarify any inconsistent data. The Aravind study coordinator is the only person who is authorized to add missing data or make any changes to the study forms. All changes should be made with a red ink pen, and then signed and dated.

7.3 Data Storage and Security

De-identified data will then be input into a database using double data entry at UCSF. Data will be stored at UCSF for about 10 years.

8. STATISTICAL ANALYSIS PLAN

Please see the **Statistical Analysis Plan (SAP)** for details on the statistical analysis.

Mycotic Antimicrobial Localized Injection

Statistical Analysis Plan

Aravind Eye Hospital, Pondicherry, India
Francis I. Proctor Foundation, University of California San Francisco, USA

Investigators:

[name], DO DNB FICO*¹

[name], DO DNB FICO*¹

[name], DO DNB FICO*¹

[name], MD²

[name]*²

*Principal Investigator

¹Aravind Eye Hospital, Pondicherry, India

² Francis I. Proctor Foundation, University of California San Francisco, San Francisco, California, USA

MALIN Statistical Analysis Plan

Table of Contents

1. Background	1
2. Sample Size and Randomization.....	1
3. Baseline Characteristics	1
4. Primary Analysis.....	1
5. Secondary Analyses	1
6. Interim Analysis.....	2

1. Background

Mycotic Antimicrobial Localized Injection (MALIN) is a randomized, double-masked, two-arm clinical trial. The purpose of this study is to determine if intrastromal injection with voriconazole in combination with topical natamycin is superior to topical natamycin alone. Study participant's eyes will be randomized to one of two treatment groups – 1.) Topical natamycin alone or 2.) Topical natamycin plus intrastromal voriconazole injections.

2. Sample Size and Randomization

If we enroll 70 study participants we estimate that we will have over 80% power to detect a 25% difference in repeat culture status (50% in the control group vs. 25% in the voriconazole group), assuming a two-tailed alpha 0.05% and no loss to follow up (since participants will be hospitalized after enrollment until the 3-day repeat cultures are taken). Participants will be randomized using random block sizes in Microsoft Excel ([name]).

3. Baseline Characteristics

Baseline characteristics between the 2 arms will be compared using Fisher exact test for categorical variables and Wilcoxon rank sum test for continuous variables.

4. Primary Analysis

The primary study analysis will be microbiological cure at 3 days. We will compare 3-day culture positivity between the two groups using a logistic regression model (dichotomous culture positive or culture negative outcome) controlling for baseline culture status. Protocol for obtaining cultures is outlined in the MOP.

5. Secondary Analyses

- We will compare BSCVA between the two groups, at the 3-month time period (between 2.5-3.5 months) using the Wilcoxon rank sum with a 2-sided alpha of 0.05. For study participants who experience perforation or undergo TPK this will be noted and a BSCVA will be performed prior to performing further surgery, this last observation will be carried forward (LOCF) as the 3-month BSCVA. An enhanced analysis using standard longitudinal modeling methods will be used to handle data from study participants who are lost to follow up.
- We will compare 7-day culture positivity between the two groups using a logistic regression model (dichotomous culture positive or culture negative outcome) controlling for baseline culture status
- Scar size as measured on clinical exam and photographs
- Corneal topography
- Corneal Thickness and scar size as measured by OCT
- IND-VFQ will be compared between the two groups controlling for baseline VFQ
- Analyses of perforations or other adverse events
- A cost effectiveness analysis will be performed

6. Interim Monitoring

A masked interim analysis will be conducted to re-evaluate sample size based on 3-day culture positivity when one-third of the data have been collected. A medical monitor will be appointed at UCSF to monitor any serious adverse events. A small DSMC at UCSF will be appointed to conduct an un-masked interim analysis to evaluate for futility or harm.

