Mycotic Antimicrobial Localized Injection (MALIN) is a randomized, masked, two-arm clinical trial. The purpose of the study is to determine differences in microbiological cure for 3-day repeat cultures between different antifungal treatments. There will be 1:1 randomization to one of these two treatment groups: 1) Topical natamycin plus intrastromal voriconazole injection or 2) Topical natamycin alone. The enrollment period will be 3 months.

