3.2 Eligibility Requirements

Only those who meet all of the inclusion criteria and none of the exclusion criteria will be enrolled in this study.

Inclusion criteria:

- Moderate to severe corneal ulcer that is smear positive for filamentous fungus
- Pinhole visual acuity worse than 20/70 in the affected eye
- Age 18 years or greater, and less than or equal to 70 years
- Basic understanding of the study as determined by the physician
- Commitment to return for follow up visits

Exclusion criteria:

- Gram stain positive for bacteria or evidence of other concomitant infection (i.e. herpes, acanthameoba)
- Impending or frank perforation at recruitment
- Involvement of sclera at presentation
- Non-infectious or autoimmune keratitis
- History of corneal transplantation or recent intraocular surgery
- No light perception in the affected eye
- Pinhole visual acuity worse than 20/200 in the unaffected eye
- Pregnant women
- Participants who are decisionally and/or cognitively impaired

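### SAP section 2 claims over 80% power from 70 participants; at 35 per arm the stated rates give about 58%

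*SAP*

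**What the plan says.** The only power statement is in SAP section 2: "If we enroll 70 study participants we estimate that we will have over 80% power to detect a 25% difference in repeat culture status". The rates and error level follow: "50% in the control group vs. 25% in the voriconazole group), assuming a two-tailed alpha 0.05". A percent sign is printed after that last figure. The section assumes that nobody is lost before the Day 3 culture, because participants are in hospital until then. It gives no formula and does not mention a number per arm.

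Four other places bear on the figure:

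- Protocol section 1.3: "There will be 1:1 randomization to one of these two treatment groups".
- SAP section 4, on the primary analysis: "We will compare 3-day culture positivity between the two groups using a logistic regression model", with baseline culture status as a covariate.
- Protocol section 3.2, first inclusion criterion: "Moderate to severe corneal ulcer that is smear positive for filamentous fungus". A positive smear is required, but not a positive culture.
- SAP section 6: "A masked interim analysis will be conducted to re-evaluate sample size based on 3-day culture positivity when one-third of the data have been collected".

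**The concern.** Thirty-five per arm is small for a comparison of 50% with 25%, and the stated power does not follow from the stated inputs. If 70 is the total and the hypothesised effect is real, an unadjusted comparison would miss it about 4 times in 10. The SAP implies fewer than 2 in 10. A null result would then be read as stronger evidence against the injection than it is. The masked sample-size re-evaluation in SAP section 6 has no formula of its own, so it could repeat the error if it reuses this calculation.

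**Working it through.** **Inputs**

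- N = 70 participants (SAP section 2), allocated 1:1 (Protocol section 1.3), so n = 70/2 = 35 per arm.
- Day 3 culture positivity p1 = 0.50 (control) and p2 = 0.25 (voriconazole), so Δ = 0.25 (SAP section 2).
- Two-sided alpha 0.05, z = 1.960. The printed 0.05% is read as 0.05 because the visual acuity comparison in SAP section 5 is made "using the Wilcoxon rank sum with a 2-sided alpha of 0.05". This reading favours the plan: taken literally, 0.0005 gives 8.6% power.
- No loss before Day 3 (SAP section 2).

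**Attempt to reproduce the SAP's figure (70 in total)**

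Pooled-variance formula, with mean rate p̄ = (0.50 + 0.25)/2 = 0.375:

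Power = Φ{[Δ − z·√(2p̄(1−p̄)/n)] / √[(p1(1−p1) + p2(1−p2))/n]}

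- √(2 × 0.375 × 0.625/35) = 0.1157, and 1.960 × 0.1157 = 0.2268.
- √[(0.25 + 0.1875)/35] = 0.1118.
- (0.25 − 0.2268)/0.1118 = 0.207, and Φ(0.207) = **58.2%**.

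Unpooled formula: 0.25/0.1118 − 1.960 = 0.276, and Φ(0.276) = 60.9%.

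| Method, 35 per arm, two-sided 0.05 | Power |
|---|---|
| Pooled z | 58.2% |
| Unpooled z | 60.9% |
| Arcsine | 59.1% |
| Chi-square, exact power | 58.9% |
| Unadjusted logistic model, Wald test | 56.9% |
| Fisher exact | 49.8% |
| Continuity-corrected z | 48.1% |

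None comes near 80%. A one-sided test at 0.05 would still give only 70.3% (pooled).

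**Sample size for 80% power at the stated rates**

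- Pooled: n = [1.960·√(2 × 0.375 × 0.625) + 0.842·√0.4375]² / 0.25² = 57.7, so 58 per arm and 116 in total.
- Unpooled: n = (1.960 + 0.842)² × 0.4375/0.0625 = 54.9, so 55 per arm and 110 in total.

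**What 35 per arm can detect**

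With control at 50%, pooled power reaches 80% when the voriconazole rate is about 19% (0.187), a difference of about 31 points instead of 25.

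**If 70 is the number per arm**

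Pooled: [0.25 − 1.960 × 0.0818]/0.0791 = 1.13, and Φ(1.13) = 87.2%. Fisher exact gives 83.1%. Either satisfies the claim, but enrolment would be 140.

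**Effect of adjusting for baseline culture**

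The planned logistic model was simulated with 35 per arm, a common odds ratio and marginal rates held at 50% and 25%. The documents give neither the share of eyes that are culture-negative at baseline nor their Day 3 positivity. Both are assumptions here, and the results are illustrative only.

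| Baseline culture-negative (assumed) | Likelihood-ratio power | Wald power |
|---|---|---|
| 0% | 60% | 56% |
| 20% | 66–68% | 64–66% |
| 30% | 68–74% | 67–72% |
| 40% | 75–83% | 73–78% |

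Ranges cover 0% to 10% Day 3 positivity among baseline-negative controls. Separate simulations differed by a point or two. Where the likelihood-ratio test reaches 80%, simulation under the null showed it rejecting roughly 7% to 8% of the time instead of 5%, so part of that apparent power is inflation.

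**The case against.** Three arguments favour the plan.

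First, 70 may have been meant per arm, which would make the statement true. That is plausible, and it would turn the defect from a wrong power into a wrong total. But the sentence speaks of enrolling 70 participants, and neither document mentions 140 or a per-arm number. The text still needs correcting on that reading.

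Second, 58% is not strictly the power of the planned test. The primary model adjusts for baseline culture status, and smear-positive eyes can be culture-negative. If baseline status is strongly prognostic, the real shortfall could be well below 22 points. This stands as a limit on the size of the problem. It does not support the stated figure: about 80% needs roughly 40% or more culture-negative at baseline, few of those positive at Day 3, and a likelihood-ratio test. The SAP assumes none of these and claims no gain from adjustment.

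Third, the masked re-evaluation at one-third of the data makes the starting number provisional. It may expose the shortfall, but it does not make the power stated for 70 correct.

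**Conclusion.** The power statement is wrong as written. With 70 in total, 1:1 allocation, 50% versus 25%, two-sided alpha 0.05 and no losses, power is about 58%, at least 20 points short of the claim. No standard two-sided test of the two proportions closes that gap. The 58% rests on an unadjusted comparison and on reading alpha as 0.05. Adjusted power is probably somewhat higher, but it cannot be fixed from the documents. If 70 is per arm, power is about 87% and the error lies in the stated enrolment. The percent sign after alpha is a minor slip and adds nothing to the weight of the point.

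**What to change.** In SAP section 2:

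1. Print alpha as 0.05.
2. State whether 70 is the total or the number per arm.
3. Give the formula and, if credit is taken for adjustment, the assumed baseline culture-negative share and the Day 3 positivity in those eyes.
4. If 70 is the total, restate along these lines: 70 participants (35 per arm) give about 58% power for 50% versus 25% at a two-sided alpha of 0.05, and 80% power only for about 50% versus 19%. If 70 is per arm, state 140 in total and about 87%.
5. Use the corrected calculation in the masked re-evaluation in SAP section 6.

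The restatement costs only wording, although the stated power looks less favourable if 70 is the total. In that case, and without credit for adjustment, a correct re-evaluation at the planned rates would point to about 116 participants, 116 − 70 = 46 more, against the 3-month enrolment period in Protocol section 1.3. Whether to enrol them is for the sponsor to decide.

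### The only significance level attached to the primary outcome is printed as 0.05% (0.0005), almost certainly a slip for 0.05; section 4 gives none, and correcting the slip leaves power at about 58%, not over 80%

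*SAP*

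**What the plan says.** SAP section 2 (Sample Size and Randomization) states: "If we enroll 70 study participants we estimate that we will have over 80% power". The assumed rates of positive repeat culture are "50% in the control group vs. 25% in the voriconazole group", and the calculation is made "assuming a two-tailed alpha 0.05% and no loss to follow up". Protocol section 1.3 gives the allocation: "There will be 1:1 randomization to one of these two treatment groups". That makes 35 per arm.

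SAP section 4 (Primary Analysis) names the method: "We will compare 3-day culture positivity between the two groups using a logistic regression model", adjusted for baseline culture status. It gives no significance level. Protocol section 8 only points to the SAP.

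The one other significance level is in SAP section 5, for 3-month BSCVA, a secondary outcome: "using the Wilcoxon rank sum with a 2-sided alpha of 0.05".

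**The concern.** 0.05% is 0.0005, one hundredth of the level used for BSCVA. Had section 4 stated 0.05, the figure in section 2 would be a harmless misprint. Section 4 is silent, so the misprint is the only level a reader can connect to the primary outcome.

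Two things depend on it. First, the primary test has no stated threshold for a claim of superiority. A primary p-value between 0.0005 and 0.05 would have to be interpreted by appeal to what the authors must have meant, and that is best settled before anyone sees results by arm. Second, SAP section 6 plans a masked re-evaluation of sample size from Day 3 culture positivity once one-third of the data are in, and an unmasked look for futility or harm. Any recalculation of sample size needs an alpha, and a futility rule based on conditional power, if one is used, would need it too.

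The same sentence also claims more than 80% power, so the check below asks whether either reading of alpha supports that claim.

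**Working it through.** **Inputs.** n = 35 per arm (70 in total, SAP section 2; 1:1, protocol section 1.3). p1 = 0.50 and p2 = 0.25 (SAP section 2). No loss before the Day 3 culture (SAP section 2). Alpha: 0.0005 as printed, or 0.05 as in SAP section 5. The tests below are unadjusted, because the documents give no baseline culture rates or correlation from which to compute power for the adjusted model.

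**Formula.** Two-proportion normal approximation with pooled null variance:

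power = Φ[(|p1 − p2| − z × s0) / s1]

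- Pooled proportion = (0.50 + 0.25)/2 = 0.375.
- s0 = √(2 × 0.375 × 0.625 / 35) = 0.1157.
- s1 = √(0.50 × 0.50/35 + 0.25 × 0.75/35) = 0.1118.

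**The plan's own figure (over 80%).** As printed, alpha = 0.0005, z = 3.481: (0.25 − 3.481 × 0.1157)/0.1118 = −1.367, so power = 8.6%. The stated figure is not reproduced.

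**After correcting alpha.** Alpha = 0.05, z = 1.960: (0.25 − 1.960 × 0.1157)/0.1118 = 0.207, so power = 58.2%. The stated figure is still not reproduced.

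**Other unadjusted methods, 35 per arm:**

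| Method | Power at 0.05 | Power at 0.0005 |
|---|---|---|
| Pooled normal approximation | 58.2% | 8.6% |
| Chi-square, exact enumeration | 58.9% | 8.3% |
| Fisher's exact | 49.8% | 5.9% |
| Logistic likelihood ratio | 60.8% | 9.5% |
| Logistic Wald | 56.9% | 6.2% |
| Continuity-corrected | 48.1% | 5.2% |
| Arcsine | 59.1% | 9.8% |
| Unpooled variance | 60.9% | 10.7% |

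One-sided 0.05, which the SAP does not specify, gives 70.3%. No variant with 70 in total reaches 80%. Reading 70 as the number per arm would give 87.2% at 0.05 (33.0% at 0.0005), but the SAP says 70 participants are enrolled.

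**Sample size for 80% power.** n per arm = [(z × √(2 × 0.375 × 0.625) + 0.842 × √(0.25 + 0.1875)) / 0.25]².

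- At 0.05: 57.7, so 58 per arm, 116 in total (66 per arm, 132 in total, with continuity correction).
- At 0.0005: 138.3, so 139 per arm, 278 in total.

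**Detectable difference.** At two-sided 0.05 with 35 per arm and a 50% control rate, power is 79.2% for a 19% rate in the injection arm and 82.1% for 18%. So 70 participants give 80% power for a difference of about 31 to 32 points, not 25.

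**What the two readings do to a result near the design effect.** With 18/35 positive in the control arm and 9/35 in the injection arm, the uncorrected chi-square test gives p = 0.027: significant at 0.05, not at 0.0005. Reaching 0.0005 would take at most 4/35 by chi-square (p = 0.0003), but at most 3/35 by Fisher (4/35 gives p = 0.0006) or by the logistic Wald test (4/35 gives p = 0.0008). These cut-offs depend on the test, and none is for the adjusted model.

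**The case against.** The strongest reply is that this is a misplaced percent sign. The figure appears once, as an input to a power estimate. The only other alpha has the same digits without the sign. Nothing in the SAP, neither a multiplicity scheme nor an alpha-spending rule, would motivate 0.0005. The stated power is also nowhere near what 0.0005 would give. All of this stands.

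It rules out a stronger reading that a reader might infer: that the trial's decision threshold is 0.0005, that the primary test therefore has about 8% power, and that p = 0.01 would be a negative trial under the SAP. The documents do not support this. Section 2 states a planning assumption. Section 4, where a decision rule belongs, contains none, so there is no rule under which to call p = 0.01 negative. The 8% and 278-participant figures follow only from taking a probable misprint literally.

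It can also be said that the larger problem in the sentence is the power claim, and that the alpha should be handled with it. That is fair: both sit in one sentence and should be corrected together. But the gap in section 4 is not a misprint and would remain after the percent sign was deleted.

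Finally, adjustment for baseline culture status could move the power. The documents give nothing from which to say how far.

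**Conclusion.** The point holds as an error in the text plus an omission. Section 2 prints a level for the primary outcome that is one hundredth of the level in section 5, almost certainly by mistake, and section 4 states none. The documents do not show that 0.0005 was ever intended.

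The consequence that survives correction is the power. At two-sided 0.05, 70 participants give about 58% (50% to 59% between Fisher and chi-square; 48% to 61% over all the two-sided methods tried), so the claim of over 80% is wrong under either reading of alpha. This rests on 1:1 allocation, no missing Day 3 cultures, the SAP's own 50% and 25%, and an unadjusted test.

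**What to change.** Make three changes to the SAP before any unmasked look:

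1. Section 2: replace the printed alpha with a two-sided alpha of 0.05 (5%).
2. Section 4: state that the treatment term in the logistic model is tested at two-sided 0.05.
3. Section 2: restate the power at that level. Either report about 58% for 70 participants and name the test used, or change the enrolment target (about 116 in total for 80% power under the same assumptions). The masked sample-size re-evaluation in section 6 should use the same alpha.

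The first two changes cost two lines of wording, with no extra patients or procedures. The third costs one recalculation. Whether to enlarge the trial is a separate decision for the sponsor, but the sentence cannot keep its present power figure.

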1. INTRODUCTION AND BACKGROUND

Fungal corneal ulcers, because of their poor outcomes and the lack of evidence to guide treatment, present a therapeutic challenge to clinicians.¹ The incidence of fungal keratitis varies by region, which is thought to be due to differences in climate as well as risk of corneal trauma.^{1,2} In the tropics, fungal infection can account for upwards of 50% of corneal ulcers.^{1,3,4} In the United States fungal keratitis ranges from 35% of corneal ulcers in South Florida⁵ to 4% in temperate climates such as Los Angeles.⁶ The Mycotic Ulcer Treatment Trial I (MUTT I), a NEI-funded randomized double masked clinical trial found that natamycin is superior to voriconazole for the treatment of filamentous fungal ulcers and in particular for *Fusarium* species.⁷ However, natamycin is fungistatic and has limited penetration into the corneal layers.⁸

Voriconazole may still be an important adjunct in the treatment of fungal ulcers. *In vitro* studies suggest that voriconazole should have good efficacy against *Aspergillus* and *Fusarium*.⁹ Intrastromal injection of voriconazole may provide steady state drug concentrations at the site of infection and avoid intervals of sub-therapeutic drug dosing. Secondly, the identity of the organism may play an important role in guiding treatment. Ulcers caused by *Aspergillus* species did equally well with topical voriconazole and natamycin, whereas those caused by *Fusarium* species had 4 lines worse visual acuity at 3 months. Possibly, *Aspergillus* ulcers will fare better when oral voriconazole is added. Thirdly, there may be presenting characteristics, such as deep stromal involvement, which could predict a benefit from intrastromal voriconazole injection.

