4.2 Ulcer Classification

Factor	Mild	Moderate	Severe
Location	Nonaxial	Central or peripheral	Central or peripheral
Area	2 mm	2–6 mm	≥6 mm
Depth	Superficial one third of stroma	Superficial two thirds of stroma	Extending to inner one third of stroma and/ or endothelial plaque

Any two of three criteria should be fulfilled.

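### The Day 3 and Day 7 culture models adjust only for baseline culture status; prespecifying baseline ulcer depth as well is a cheap improvement that gives a modest power gain if depth is prognostic

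*SAP*

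**What the plan says.** SAP section 4 compares Day 3 culture between arms by logistic regression ("dichotomous culture positive or culture negative outcome) controlling for baseline culture status"). SAP section 5 repeats the model for Day 7: "We will compare 7-day culture positivity between the two groups using a logistic regression model", again with baseline culture status as the only covariate. No sensitivity analysis with further covariates and no analysis by depth is planned. Randomisation is blocked (Protocol 3.3, SAP section 2), and no stratification factor is named. SAP section 3 tests baseline balance but does not say what follows if the arms differ.

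Depth enters the trial through eligibility. Only moderate to severe ulcers qualify (Protocol 3.2), graded by location, area and depth (Protocol 4.2). The severe depth category is "Extending to inner one third of stroma and/ or endothelial plaque". An eye is graded on meeting two of the three factors. Slit lamp examination precedes the Day 0 scraping (Protocol 4.4.1), and OCT is done before randomisation (Protocol 3.4.1).

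The Introduction makes two remarks that bear on depth. One is that "natamycin is fungistatic and has limited penetration into the corneal layers". The other is that deep stromal involvement is a presenting feature that might identify eyes which benefit from the injection.

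**The concern.** Both arms receive natamycin. If the drug reaches deep stroma poorly, deep ulcers may stay culture positive at Day 3 more often, at least on natamycin alone. In that case a model without depth leaves explainable variation in the outcome as noise, and with 35 eyes per arm the arms can differ noticeably in depth by chance.

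The protocol itself shows how such imbalance complicates interpretation. Its Introduction qualifies the result of a previous randomised trial of intrastromal voriconazole because the arms differed in the number of central ulcers. That concerned location rather than depth, but the difficulty is the same. If depth differs here, any adjustment chosen after unmasking would be open to dispute; prespecifying it avoids that. What is at stake is some efficiency and a cleaner interpretation, not the validity of the test.

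**Working it through.** **Inputs from the documents.** "If we enroll 70 study participants we estimate that we will have over 80% power to detect a 25% difference"; rates "50% in the control group vs. 25% in the voriconazole group"; "assuming a two-tailed alpha 0.05% and no loss to follow up", with alpha read as 0.05; and "There will be 1:1 randomization to one of these two treatment groups", so 35 eyes per arm.

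**The plan's own power figure.** Pooled two-proportion formula, two-sided 0.05:

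z = [0.25 × √35 − 1.96 × √(2 × 0.375 × 0.625)] / √(0.25 + 0.1875) = (1.479 − 1.342) / 0.661 = 0.207, so power = Φ(0.207) = 58.2%.

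Other methods give 60.9% (unpooled), 59.1% (arcsine), 56.7% (Wald log odds ratio) and 49.8% (Fisher exact). The stated power is not reproduced with 70 in total; with 70 per arm it would be 87.2%. Any gain from depth therefore starts from about 60%, not 80%.

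**Effect of adding depth to the Day 3 model.** Simulated trials of 70 eyes, marginal rates held at 50% and 25%, likelihood-ratio test of treatment at 0.05. Everything else is assumed:

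- Set A (4,000 trials per cell): 20% of eyes baseline culture negative, with 5% Day 3 positivity; half of eyes deep.
- Set B (2,000 trials per cell): 80% baseline culture positive, odds ratio 4 for baseline culture; 30% or 50% deep.

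Power without → with depth (gain in points):

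| Depth odds ratio | Set A | Set B, 30% deep | Set B, 50% deep |
|---|---|---|---|
| 1 | 65.2 → 64.8 (−0.4) | 61.2 → 61.2 (0.0) | 62.0 → 61.8 (−0.2) |
| 2 | 66.0 → 66.8 (0.8) | 61.8 → 64.2 (2.4) | 62.0 → 65.9 (3.9) |
| 3 | – | 62.0 → 66.2 (4.2) | 61.4 → 66.3 (4.9) |
| 4 | 65.6 → 69.8 (4.2) | – | – |
| 5 | – | 61.0 → 68.4 (7.4) | 61.2 → 70.0 (8.8) |
| 8 | 64.6 → 73.5 (8.9) | – | – |
| 10 | – | 63.4 → 74.2 (10.8) | 59.6 → 73.6 (14.0) |
| 12 | 64.7 → 77.1 (12.4) | – | – |

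A third set, with odds ratio 6 for baseline culture, gave no material change at depth odds ratio 1, then gains of about 1–3 points at 2–3, 3–5 at 4 and 8–10 at 8.

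The Monte Carlo standard error of one power estimate is about √(0.65 × 0.35 / 4000) = 0.75 points in Set A and √(0.62 × 0.38 / 2000) = 1.1 points in Set B. Gains of about a point are not distinguishable from none.

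**Type I error.** Set A: 4.8–6.0% without depth, 4.7–5.9% with it. Set B: 4.6–5.8% without, 4.8–6.6% with. Third set: about 5–7% in both models.

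**Events per parameter.** Expected Day 3 positives = 35 × 0.50 + 35 × 0.25 = 26.25. With treatment, baseline culture and depth: 26.25 / 3 = about 9 each.

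**Chance imbalance.** If half of eyes are deep, the SD of the between-arm difference in the deep share is √(2 × 0.25 / 35) = 0.12. Around a 50% control rate, a depth odds ratio of 2 means 58.6% against 41.4%, so a 1-SD imbalance moves the risk difference by 0.12 × 17.2 = about 2 points. At 4 it is 66.7% against 33.3%, giving 0.12 × 33.3 = 4 points. The target difference is 25 points.

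**The case against.** Adjusting for the baseline value of the outcome is a conventional, prespecified choice, and nothing in the documents contradicts it. The objections to going further have force:

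- **A reader might infer that the protocol names depth as prognostic.** It does not. It raises deep involvement, tentatively, as a possible marker of benefit from injection. That is effect modification, which a main-effect term does not address. The prognostic link is an inference from natamycin's penetration, and the documents do not say how strongly depth predicts a positive scrape from the ulcer's edge and base. This stands.
- **A reader might infer that omitting depth biases the primary comparison.** It does not. Chance imbalance under randomisation is random error, which the test already allows for; the planned model's simulated type I error is about 5–7%.
- **A reader might infer that every eye already has a recorded depth grade.** The two-of-three rule lets an eye qualify on location and area, and the contents of the baseline form are not in the documents. Baseline examination and OCT make depth obtainable, no more.
- **The gain may be small.** Restricting entry to moderate and severe ulcers may narrow the spread of depth, although the proposed cut is the boundary between those two grades. In Set A the planned covariate is already strong: culture-positive control eyes have (0.50 − 0.20 × 0.05) / 0.80 = 61% positivity against 5%, an odds ratio of about 30.
- **The adjustment is not quite free.** There are about 9 events per parameter, and type I error reached 6.6% in one setting. The odds ratio also becomes conditional on depth, though the planned one is already conditional on baseline culture.

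These points limit the claim. They leave the case for a low-cost prespecified covariate intact.

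**Conclusion.** A cheap improvement, not an error in the plan. Both culture models omit a baseline feature that belongs to the entry grading and should be available before randomisation. If depth is prognostic for Day 3 culture, prespecifying it gains about 1–5 points of power at a depth odds ratio of 2–3, 3–9 at 4–5 and 8–14 at 8–10; if it is not, nothing is gained and little is lost. The depth odds ratios, the 30% or 50% deep share and the baseline culture assumptions are not in the documents.

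The figures are for Day 3 only. The documents give no Day 7 rates, and treatment is discretionary after the Day 3 scraping, so the Day 7 gain is not quantified.

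A reader might also infer that depth adjustment rescues the trial's power. It does not: the best scenario reaches 77.1%, at an odds ratio of 12. The gap between the stated power and about 58% is a separate and larger problem.

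**What to change.** Before unmasking, change the covariates in SAP sections 4 and 5 to baseline culture status and baseline ulcer depth, coded yes/no for the severe depth category of Protocol 4.2. State in the SAP that depth is recorded for every eye before randomisation, including eyes that qualify on location and area. Keep the model without depth as a sensitivity analysis. If the sponsor wants to address the Introduction's suggestion about who benefits, add a treatment-by-depth analysis labelled exploratory.

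The cost is one SAP clause, a check that the baseline form captures depth, and one extra parameter. The sample-size statement should be corrected separately.
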